## 8.5. Exclusion Criteria

1. Active smoldering MM.
2. Active plasma cell leukemia.
3. Documented systemic amyloid light chain amyloidosis.
4. Active central nervous system (CNS) MM.
5. Pregnancy or breastfeeding.
6. Radiation, chemotherapy, or immunotherapy or any other anticancer therapy  $\leq 2$  weeks prior to Cycle 1 Day 1, and radio-immunotherapy 6 weeks prior to Cycle 1 Day 1.
7. Active graft vs. host disease (after allogeneic stem cell transplantation) at Cycle 1 Day 1
8. Life expectancy of  $< 4$  months.
9. Major surgery within four weeks prior to Cycle 1 Day 1.
10. Active, unstable cardiovascular function:
  - a. Symptomatic ischemia, or
  - b. Uncontrolled clinically-significant conduction abnormalities (e.g., patients with ventricular tachycardia on antiarrhythmics are excluded; patients with 1st degree atrioventricular (AV) block or asymptomatic left anterior fascicular block/right bundle branch block (LAFB/RBBB) will not be excluded), or
  - c. Congestive heart failure (CHF) of New York Heart Association (NYHA) Class  $\geq 3$ , or
  - d. Myocardial infarction (MI) within 3 months prior to Cycle 1 Day 1.
11. Active, uncontrolled hypertension.

12. Uncontrolled active infection requiring parenteral antibiotics, antivirals, or antifungals within one week prior to first dose.
13. Known HIV seropositive.
14. Known active hepatitis A, B, or C infection; or known to be positive for HCV RNA or HBsAg (HBV surface antigen).
15. Prior malignancy that required treatment, or has shown evidence of recurrence (except for non-melanoma skin cancer or adequately treated cervical carcinoma in situ) during the 5 years prior to enrollment. Cancer treated with curative intent > 5 years previously and without evidence of recurrence will be allowed.
16. Active GI dysfunction interfering with the ability to swallow tablets, or any GI dysfunction that could interfere with absorption of study treatment.
17. Grade  $\geq 3$  peripheral neuropathy, and Grade  $\geq 2$  painful neuropathy, within 21 days prior to Cycle 1 Day 1.
18. Serious, active psychiatric or medical conditions which, in the opinion of the Investigator, could interfere with treatment.
19. Participation in an investigational anti-cancer study within 21 days prior to Cycle 1 Day 1.
20. Receipt of transfusions as follows:
  - a. Platelet infusion within 1 week prior to Cycle 1 Day 1.
  - b. RBC transfusion within 2 weeks prior to Cycle 1 Day 1.
21. Receipt of the following blood growth factors within 2 weeks prior to Cycle 1 Day 1: Granulocyte colony stimulating factor (G-CSF), granulocyte-macrophage colony stimulating factor (GM-CSF), erythropoietin (EPO), or megakaryocyte growth factor.
22. Known intolerance to or contraindications for glucocorticoid therapy at Cycle 1 Day 1.
23. Prior exposure to a SINE compound, including selinexor.
24. Unable or unwilling to comply with protocol requirements, including providing a 24-hour urine samples at the required study time points.

## **8.6. Screen Failures**

Patients who sign an informed consent form and do not receive study treatment for any reason are defined as screen failures. For all screen failures, the Investigator will enter the screening number, patient initials; and reason(s) for screen failure onto electronic case report forms (eCRFs). Screen failures will be replaced. Screen failures may be re-screened.

## **8.7. Study Patient Numbers**

Each patient will be assigned a unique study number and will keep this number for the duration of the study. Patient numbers will not be reassigned or reused for any reason.

Patients will be identified to the Sponsor only by their assigned number, initials, date of birth, and sex. The Investigator must maintain a patient identification master log.

## **8.8. Study Patient Number**

Each patient will be assigned a unique study number and will keep this number for the duration of the study. Patient numbers will not be reassigned or reused for any reason. Patients will be identified to Karyopharm only by their assigned number, initials, year of birth (as allowed by national and local regulatory authorities), and sex. The Investigator must maintain a patient identification master log.

## **9. METHODS OF ASSESSMENT AND ENDPOINTS**

### **9.1. Standard Study Assessments**

All assessments should be performed as outlined in [Table 1](#).

#### **9.1.1. Demographic Data**

During Screening, patient demographic data will be collected. These data include year of birth, age, gender, race, and ethnicity.

#### **9.1.2. Medical History**

A complete medical history will be obtained from each patient. Medical history includes historic MM assessment values (Day -30 and Day -60), baseline symptoms as well as a detailed history of prior procedures for MM and other prior cancer therapies (i.e., transplant, chemotherapy, hormonal therapy, immunotherapy, biotherapy, radiotherapy, and surgery) including start and stop dates, best response, disease progression dates (during or after therapy), as well as discontinuations due to intolerability or toxicity. Smoking history will be recorded. Data should be reviewed by the Investigator prior to dosing on Cycle 1 Day 1.

#### **9.1.3. Concomitant Medications**

Concomitant medications will be documented for each patient at each scheduled visit. A detailed history of medications will be documented in the eCRF. Subsequently, at each study visit, patients will be asked whether they have taken any medication other than the study medication (from Screening through the end of the study). All concomitant medications including dietary supplements, over-the-counter medications, and oral herbal preparations, as well as changes in medication, will be recorded on the eCRFs.

Supportive care (such as appetite stimulants, anti-emetics, and anti-diarrheals, etc.) is encouraged (see [Section 11.4.2](#)).

#### **9.1.4. Physical Examination**

Full physical examinations (PE) during Screening and the EoT Visit will be performed. All other PEs during the study should be symptom-directed PEs. Significant findings that were present prior to the signing of informed consent must be included on the medical history page on the patient's CRF. Significant new findings, including the presence of plasmacytomas,

that begin or worsen after informed consent must be recorded on the Adverse Event or Plasmacytoma page of the patient's CRF.

PEs, unless otherwise noted, will include the following:

- Height (without shoes) in centimeters (cm) measured during Screening only
- Body weight (indoor clothing without shoes) in kilograms (kg)
- Body temperature
- Systolic and diastolic BP and pulse rate measured at each visit after the patient has been in a supine or sitting position for 5 minutes. BP should be assessed on the same arm at each visit.

Information about the PE must be present in the source documentation at the study site. Clinically relevant findings made after the start of selinexor plus dexamethasone dosing, which meet the definition of an AE, must be recorded on the AE eCRF.

### 9.1.5. ECOG Score

An ECOG Score Assessment (see [Appendix 1](#)) will be performed during Screening, Day 1 of each cycle, and the EoT visit.

## 9.2. Multiple Myeloma Disease Specific Assessments

Patient response will be assessed by the procedures summarized in [Table 4](#) and graded according to the IMWG response criteria summarized in [Table 10 \(Appendix 3\)](#). Per IMWG, quantitative Ig levels by nephelometry may be used in place of SPEP for routine M-protein measurements for patients with IgA or IgD myeloma. Also, per IMWG, response may be confirmed if the patient fails to provide 24-hour urine sample collection after Screening activities occur. All MM assessments outlined in this protocol are required to be performed at each study visit, prior to dosing. If MM assessments are collected at unscheduled times, those results must be documented in the eCRF as unscheduled visits. This includes SPEP, UPEP, serum FLC,  $\beta_2$  microglobulin, quantitative Ig, and serum/urine protein immunofixation. Results of pre-screening MM assessments at Day -30 (window: Screening – 2 weeks) and Day -60 ( $\pm 15$  days) will also be provided.

SPEP with serum protein immunofixation, quantitative Ig, serum FLC, and 24-hour UPEP, with immunofixation, must be collected at each required time point. An aliquot of the blood and urine samples should be retained. If the local laboratory results indicate a CR or sCR, sequential MM disease assessment samples, per IMWG, will be collected. The sequential samples will be split – one aliquot of each sample will be sent to the local lab while the other aliquots, along with the initial assessment aliquots, will be sent to the central laboratory to confirm CR or sCR. If the results do not indicate CR or sCR, then the aliquots may be destroyed. Refer to the *Study Manual* for details.

All disease assessments (SPEP, UPEP, FLC, quantitative Ig, and serum/urine protein immunofixation) should be performed regardless of the diagnosis that is being followed (e.g., 24 hour UPEP collection must be collected at each time point outlined in the protocol even if the patient is being followed by SPEP, Ig or FLC).

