## 8.4. Inclusion Criteria

Patients must meet all of the following inclusion criteria to be eligible to enroll in this study:

1. Written informed consent in accordance with federal, local, and institutional guidelines.
2. Age  $\geq$  18 years at the time of signing informed consent.
3. Measurable MM based on IMWG guidelines as defined by at least one of the following:
  - a. Serum M-protein  $\geq$  0.5 g/dL by serum electrophoresis (SPEP) or, for IgA myeloma, by quantitative IgA
  - b. Urinary M-protein excretion  $\geq$  200 mg/24 hours
  - c. FLC  $\geq$  100 mg/L, provided that the FLC ratio is abnormal.
  - d. If serum protein electrophoresis is felt to be unreliable for routine M-protein measurement, then quantitative Ig levels by nephelometry is acceptable.
4. Patients must have previously received  $\geq$  3 anti-MM regimens including: an alkylating agent, lenalidomide, pomalidomide, bortezomib, carfilzomib, daratumumab, and a glucocorticoid. There is no upper limit on the number of prior therapies provided that all other inclusion/exclusion criteria are met.
5. MM refractory to previous treatment with one or more glucocorticoids, parenteral PI (i.e., bortezomib and/or carfilzomib), IMiD (i.e., lenalidomide and/or pomalidomide), and daratumumab. Refractory is defined as  $\leq$  25% response to therapy, or progression during therapy or progression within 60 days after completion of therapy.
6. Multiple myeloma that is refractory to the patient's most recent anti-MM regimen. (Documented severe intolerance to the patient's last therapy is allowed upon approval by the Medical Monitor.)
7. Any clinically significant non-hematological toxicities (except for peripheral neuropathy as described in exclusion criterion #17) that patients experienced from treatments in previous clinical studies must have resolved to Grade  $\leq$  2 by Cycle 1 Day 1.
8. Adequate hepatic function within 21 days prior to Cycle 1 Day 1: total bilirubin  $<$  2x upper limit of normal (ULN) (except patients with Gilbert's syndrome who must have a total bilirubin of  $<$  3x ULN), AST  $<$  2.5x ULN and ALT  $<$  2.5x ULN.
9. Adequate renal function within 21 days prior to Cycle 1 Day 1: estimated creatinine clearance of  $\geq$  20 mL/min, calculated using the formula of Cockcroft and Gault.

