**Table 4: Multiple Myeloma Disease-specific Assessments**

Procedure	Notes
SPEP with M-spike quantification, and serum protein immunofixation	Per IMWG.
UPEP (24-hour urine for total protein) with M-spike quantification and urine protein immunofixation	
Per IMWG. If the patient fails to provide the 24-hour urine sample, this should be documented. All attempts should be made to collect the 24-hour urine sample at the required time points.
 
UPEP must be determined from a urine sample collected for 24 hours – no other method is acceptable.
 
UPEP must be performed at each time point outlined in the protocol even if the patient is being followed by SPEP.

Serum FLC	Per IMWG.
Quantitative Ig levels	
Per IMWG.
 
For IgA and IgD myelomas, quantitative immunoglobulin measurements are preferred for disease assessments; the same percentage changes apply as for serum M-spike. Only nephelometry can be used for the response assessment, and SPEP and nephelometric values cannot be used interchangeably (Durie et al., 2006).

$\beta_2$ -microglobulin	For MM staging ( Appendix 2 ), not for assessing response
Skeletal survey	
A skeletal survey (using x-rays and/or other clinically appropriate imaging modalities [MRI, whole body CT, or PET/CT]), as determined by the Investigator, will be performed within 45 days of C1 D1 and as clinically indicated, per Investigator discretion, during the study. The skeletal survey should include a lateral radiograph of skull, anteroposterior and lateral views of the spine, and anteroposterior views of the pelvis, ribs, femora, and humeri. Results will be read by the local laboratory.
 
If lytic bone lesions or plasmacytomas are observed at Screening, their number and size should be recorded in the CRF. Bone lesions and/or plasmacytomas seen at baseline should be re-assessed during the study at a frequency determined by the Investigator, using the same imaging modality that was used at Screening.
 
 
• For patients without soft tissue plasmacytomas (i.e., bone lesions only), skeletal survey by X-rays or low-dose CT should be performed. Contrast is not required.
 
• For patients with soft tissue plasmacytomas, skeletal survey by X-rays or low-dose CT should be performed (contrast not required) and in addition MRI or CT or PET/CT, usually requiring contrast enhancement, should be performed.
 

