### APPENDIX 3. INTERNATIONAL MYELOMA WORKING GROUP RESPONSE CRITERIA, MYELOMA

**Table 10: International Myeloma Working Group Response Criteria (Kumar 2016)**

Standard IMWG Response Criteria 	
Response Subcategory	Response Criteria
Complete response (CR)	Negative immunofixation of serum and urine, disappearance of any soft tissue plasmacytomas (SPDs), and < 5% plasma cells in bone marrow aspirates
Stringent complete response (sCR)	CR as defined above plus normal FLC ratio  and absence of clonal cells in bone marrow biopsy by immunohistochemistry ( $\kappa/\lambda$ ratio $\leq 4:1$ or $\geq 1:2$ for $\kappa$ and $\lambda$ patients, respectively, after counting $\geq 100$ plasma cells  )
Very good partial response (VGPR)	Serum and urine M-protein detectable by immunofixation but not on electrophoresis or $\geq 90\%$ reduction in serum M-protein plus urine M-protein level < 100 mg per 24 hr
Partial response (PR)	$\geq 50\%$ reduction of serum M-protein plus reduction in 24-hr urinary M-protein by $\geq 90\%$ or to < 200 mg/24 hr. If the serum and urine M-protein are not measurable, a $\geq 50\%$ decrease in the difference between involved and uninvolved FLC levels is required in place of the M-protein criteria. If serum and urine M-protein and serum FLC assay are not measurable, $\geq 50\%$ reduction in plasma cells is required in place of M-protein, provided baseline bone marrow plasma cell percentage was $\geq 30\%$ . In addition to the above criteria, if present at baseline, a $\geq 50\%$ reduction in the size (SPD) of soft tissue plasmacytomas is also required. 
Minimal response (MR)	$\geq 25\%$ but < 49% reduction of serum M-protein and reduction in 24-hr urine M-protein by 50–89%. In addition to the above criteria, if present at baseline, a $\geq 50\%$ reduction in the size (SPD) of soft tissue plasmacytomas is also required. 
Stable disease (SD)	Not recommended for use as an indicator of response; stability of disease is best described by providing the TTP estimates. Not meeting criteria for CR, VGPR, PR, MR, or PD.
Progressive disease (PD) 	Any 1 or more of the following criteria: Increase of 25% from lowest confirmed response value in 1 or more of the following criteria: Serum M-protein with absolute increase of $\geq 0.5$ g/dL;

Standard IMWG Response Criteria	
Response Subcategory	Response Criteria

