 Per IMWG, quantitative Ig levels by nephelometry may be used in place of SPEP for routine M-protein measurement for patients with IgA or IgD myeloma. Also, per IMWG, response may be confirmed if the patient fails to provide 24-hour urine sample collection after screening activities occur. See “Practical considerations for application of IMWG consensus criteria” section of the guidelines (page e340; Kumar, 2016).

 Derived from international uniform response criteria for MM ([Durie 2011](#)). MR definition and clarifications derived from Rajkumar ([Rajkumar 2011](#)). When the only method to measure disease is by serum FLC levels: CR can be defined as a normal FLC ratio of 0.26 to 1.65 in addition to the CR criteria listed previously. VGPR in such patients requires a  $\geq 90\%$  decrease in the difference between involved and uninvolved FLC levels. All response categories require 2 consecutive assessments made at any time before the institution of any new therapy; all categories also require no known evidence of progressive or new bone lesions or extramedullary plasmacytomas if radiographic studies were performed. Radiographic studies are not required to satisfy these response requirements. Bone marrow assessments do not need to be confirmed. Each category, except for SD, will be considered unconfirmed until the confirmatory test is performed. The date of the initial test is considered as the date of response for evaluation of time dependent outcomes such as DOR.

 All recommendations regarding clinical uses relating to serum FLC levels or FLC ratio are based on results obtained with the validated Freelite test (Binding Site, Birmingham, United Kingdom).

 Presence/absence of clonal cells on immunohistochemistry is based upon the  $\kappa/\lambda$  ratio. An abnormal  $\kappa/\lambda$  ratio by immunohistochemistry requires a minimum of 100 plasma cells for analysis. An abnormal ratio reflecting presence of an abnormal clone is  $\kappa/\lambda$  of  $> 4:1$  or  $< 1:2$ .

-  Plasmacytoma measurements should be taken from the CT portion of the PET/CT, or MRI scans, or dedicated CT scans where applicable. For patients with only skin involvement, skin lesions should be measured with a ruler. Measurement of tumor size will be determined by the SPD.

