4. EFFICACY

Patient response at each time point will be assessed centrally by an IRC according to the IMWG response criteria (*Kumar 2016*) for MM. Unless otherwise specified, MM response assessment refers to assessment determined by IRC. The primary endpoint (ORR) is based on these IRC assessed responses in the mITT population.

Documentation of response requires two consecutive readings of the applicable disease parameter (serum M-protein, urine M-protein, serum FLC, or quantitative immunoglobulin level), performed at any time with no minimum interval required between the two readings. The date of response or PD will be assigned to the earlier date of the two independent samples, unless PD is based on an unambiguous criterion such as a new plasmacytoma lesion.

If a patient had one PD assessment but was not subsequently confirmed, unless IRC considers the progression assessment unambiguous, it is not considered a PD (*Kumar 2016*).

Unless otherwise specified, efficacy analyses will use the mITT population. Analyses for the primary efficacy endpoint of ORR and the key secondary efficacy endpoints of DOR, CBR, and duration of clinical benefit will be repeated in the other efficacy populations and additional analysis populations. If relevant, selected efficacy analyses for other efficacy endpoints will be repeated in selected additional analysis populations.

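### The missing-urine waiver is not limited to patients without measurable baseline urine M-protein, and the SAP leaves open how it applies when both serum and urine are measurable

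*Protocol*

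**What the plan says.** **The waiver.** Protocol 9.2 states, with attribution to IMWG, that "response may be confirmed if the patient fails to provide 24-hour urine sample collection after Screening activities occur". Footnote 2 to Table 10 (Appendix 3) repeats this and points to a guideline section that is not reproduced. Neither place mentions baseline urine M-protein, response category or number of missed collections.

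**The response definitions.** Table 10 makes urine part of the response. For PR it asks for a serum fall of at least 50%, in the form "reduction of serum M-protein plus reduction in 24-hr urinary M-protein by" at least 90%, or to below 200 mg/24 hr. MR needs a urine fall of 50–89%. VGPR by the percentage route needs urine below 100 mg/24 hr. CR needs negative urine immunofixation.

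**Entry.** Inclusion criterion 3 in Protocol 8.4 reads "Measurable MM based on IMWG guidelines as defined by at least one of the following", and urine M-protein of at least 200 mg/24 hours is one of the options. Patients measurable in urine, alone or together with serum, can therefore enrol.

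**The SAP.** Section 4 says: "Documentation of response requires two consecutive readings of the applicable disease parameter (serum M-protein, urine M-protein, serum FLC, or quantitative immunoglobulin level". It contains no urine waiver.

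**Collection.** Table 4 says "All attempts should be made to collect the 24-hour urine sample at the required time points" and asks that a failure be documented. Exclusion criterion 24 removes patients who are "Unable or unwilling to comply with protocol requirements, including providing a 24-hour urine samples at the required study time points".

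**The concern.** The waiver removes one condition for response when a measurement is missing. For a patient whose urine M-protein was never measurable, little is lost. For a patient with measurable urine at baseline, the missing result may be the one that would have denied the response.

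The collection requirements make missing urine less likely, but none of them says that a response lacking urine is not counted. Protocol 13.3.8 sends missing data to the SAP. The readable rules in SAP 2.2 cover summary tables, dates, and AE relationship and severity, not a missing component of a response.

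The trial is open-label and single-arm, and its only formal test compares ORR with a fixed 10%. An error that can only raise ORR therefore bears directly on the claim. CBR and the set of responders used for DOR are touched in the same way.

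**Working it through.** **1. Which patients are exposed.**

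- *Urine is the only measurable parameter.* Under SAP 4 the applicable parameter is urine M-protein, and two readings are required. The SAP protects this patient.
- *Serum measurable, urine below 200 mg/24 hr at baseline.* Urine was not measurable disease, so the waiver does limited harm.
- *Both measurable.* The SAP list is joined by *or*. Two serum readings can satisfy it, and the protocol waiver covers the urine. The texts do not settle this case.

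Illustration of the third case (invented values): baseline serum 1.5 g/dL and urine 1,000 mg/24 hr. Serum falls 55%. Urine falls to 900 mg/24 hr, that is (1,000 − 900)/1,000 = 10%. With the urine result, the patient meets neither PR (≥90% or <200 mg/24 hr) nor MR (50–89%). If the urine is never supplied after Screening, the serum condition for PR is met and the waiver permits confirmation.

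**2. Which categories.** ORR changes only when the urine condition for PR would have failed. A true PR called VGPR is still a responder. A false MR affects CBR, not ORR. For CR and sCR, Protocol 7.1 and 9.2 and SAP 1.1 require central-laboratory confirmation. The assessments listed in Protocol 7.1 and SAP 1.1 include UPEP and urine immunofixation, and Protocol 7.1 adds select VGPR. The exposure is therefore mainly MR, PR and VGPR.

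**3. The decision threshold.** The target is N = 122 (Synopsis, Study Numbers). The alternative ORR and power behind it are redacted, so that figure cannot be reproduced. SAP 4.1.2 declares success if the exact two-sided 95% lower bound exceeds 10%. The lower bound is the 0.025 quantile of Beta(x, n − x + 1):

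- x = 19, n = 122: 9.64%, fails
- x = 20, n = 122: 10.31%, passes (20/122 = 16.4%)

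One patient is worth 1/122 = 0.82 percentage points. At N = 130 the threshold is 21.

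**4. How many responders could lack urine.** The documents give neither the share with measurable urine nor the rate of missed collections. Assumptions: 20% apparent responders (Part 1 showed 20–21%), 20–40% of them with measurable baseline urine, and urine missing at the response or confirming reading in 10–30%.

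- Responders: 122 × 0.20 = 24.4
- Low: 24.4 × 0.2 × 0.1 = 0.49
- High: 24.4 × 0.4 × 0.3 = 2.93

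That is 0.4 to 2.4 points of ORR (0.49/122 and 2.93/122). It counts responders without urine. Some of them would have met the urine condition, so it is a ceiling on false responses under these rates.

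**5. Effect on the test.** With 24, 25 or 26 responders, 5, 6 or 7 would have to be reclassified to reach 19 and fail. The high figure of about 3 leaves 24 − 3 = 21, which still passes. With 20, 21 or 22 responders, reclassifying 1, 2 or 3 reverses the conclusion.

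**6. Effect on the error rate.** With 20 or more of 122 required and a true ORR of 10%, the chance of success is 1.9%. If false responses added 1, 2 or 3 points, it would be 4.5%, 9.2% or 16.3%. With 10% apparent responders, the rates in step 4 give at most 12.2 × 0.4 × 0.3 = 1.46 patients, or 1.2 points. Only the first of these figures lies within the assumed range.

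**The case against.** A reader might infer that missing urine simply counts as a response in the primary ORR. The documents do not say so. The protocol word is *may*, the serum and other criteria must still be met, and the IRC decides. The SAP governs the primary analysis and has no waiver, and nothing says the protocol sentence overrides it. All of this stands, and it is why the point is confined to patients measurable in both serum and urine.

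There is also a narrower reading of *confirmed*. Footnote 3 to Table 10 separates the first test showing a response from its confirmatory test. On that reading the first assessment must satisfy Table 10 with urine, and only the second may lack it. The patient in the illustration would then never have a PR to confirm. This would shrink the exposure, but neither document states it.

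The cited guideline section, the IRC Charter and the Study Manual are not available here, and the list of supportive ORR analyses in SAP 4.1.3 is redacted. A limit on the waiver or a sensitivity analysis may exist in one of them. If a limit exists, the protocol and SAP should state it, because the waiver appears in the protocol without one.

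Finally, exclusion 24 and the collection rules suggest that few samples will be missed. That lowers the expected size but does not settle the rule.

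**Conclusion.** The point holds in limited form. Protocol 9.2 and footnote 2 to Table 10 allow confirmation without the 24-hour urine and do not exclude patients with measurable baseline urine. SAP 4 does not resolve the case of a patient measurable in both serum and urine. There, mainly at MR, PR and VGPR, a missing result can work in the patient's favour, and any error in ORR is upward.

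The size cannot be derived from the documents. The ceiling of about 0.5 to 3 of roughly 24 responders rests entirely on assumed rates. It would not overturn a result near 24 of 122, but it could matter near 20 of 122.

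Two stronger readings are not supported. One is that the primary ORR is shown to be inflated by 0.4 to 2.4 points, which treats every responder without urine as false. The other is that CR and sCR are equally exposed, which overlooks the central-laboratory confirmation.

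**What to change.** Reconcile Protocol 9.2 and footnote 2 to Table 10 with SAP 4, and carry the same rule into the IRC instructions:

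- The waiver applies only to patients with baseline urine M-protein below 200 mg/24 hr.
- For patients at or above 200 mg/24 hr, a time point without the urine result can neither establish nor confirm MR, PR or VGPR in the primary analysis. The patient stays in the mITT denominator at the best category that complete data support.
- Report the number of responses confirmed without urine, and give ORR under the unrestricted waiver as a sensitivity analysis.

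Barring VGPR, CR or sCR without urine in every patient is not needed. It would depart from a rule that the protocol attributes to a guideline that cannot be checked here.

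The cost is one sentence in each place and one extra analysis. No new procedure is needed, because urine is already required at every response time point. ORR may come out slightly lower, and a few true responders whose sample was lost may be downgraded. The sensitivity analysis shows how many.
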